#### 4.4.3 Patient data

The following patient data were to be recorded in the eDRF:

Patient demographics and socio-demographics

- Medical history and PD history
- Previous PD medication and add-on PD treatment during LCIG treatment
- Concomitant disease and medication
- LCIG treatment
- Clinical PD status

## 4.4.4 Patient reported outcomes (PROs)

## Parkinson's Disease Quality of Life Questionnaire (PDQ-8)

Using 8 items patients were asked to state how often they had encountered certain problems during the last month using the following rating scale: Never (0), occasionally (1), sometimes (2), often (3), always or cannot do at all (4).

Each of the eight items will be evaluated separately as a score ranging from 0 to 100. Thus, the score for each item will be calculated as the respective value divided by 0.04.

The *PDQ-8 summary index* will be analyzed and is derived as the sum of the single items divided by 0.32. Like that, the PDQ-8 summary index is normalized to take values between 0 and 100. In case of missing items the PDQ-8 summary index will not be calculated.

A higher score/summary index indicates a higher impairment of quality of life.

# Questionnaire for Impulsive-Compulsive Disorders in Parkinson's Disease - Rating Scale (QUIP-RS)

The QUIP-RS is a fairly novel self-administered rating scale for the evaluation of the symptoms of impulsive compulsive disorders (ICDs) which may occur in PD patients under dopaminergic drug therapy.

QUIP-RS uses a 5-point Likert scale upon which each symptom is rated based on frequency (Never (0), Rarely (1), Sometimes (2), Often (3), Very often (4)). There are four primary questions, related to the 4 ICDs (compulsive gambling, buying, eating, and sexual behavior), and 3 related disorders (medication use, punding, and hobbyism). The total QUIP-RS score ranges from 0 to 112.

The following scores will be auto calculated in the eCRF, each as sum of the respective categories:

- 1. Compulsive gambling
- 2. Sexual behavior
- 3. Buying
- 4. Eating
- 5. Hobbyism-Punding
- 6. PD medication
- 7. Total ICD scores (1.-4.)
- 8. Total QUIP-RS score (1.- 6.)

A higher score denotes greater severity.

#### Parkinson's Disease Sleep Scale-2 (PDSS-2)

The purpose of the PDSS-2 scale is to characterize the various aspects of nocturnal sleep problems in PD patients. The PDSS-2 instrument has been shown to be reliable, valid, precise, and a potentially treatment responsive tool for measuring nocturnal disabilities and sleep disorders in PD. PDSS-2 consists of 15 questions evaluating motor and non-motor symptoms at night and upon wakening, as well as disturbed sleep grouped into 3 domains: motor symptoms at night (items 4, 5, 6, 12, 13), PD symptoms at night (items 7, 9, 10, 11, 15), and disturbed sleep (items 1, 2, 3, 8, 14).

The frequency is assessed for the 15 sleep problems based on a 5-point Likert-type scale (ranging from 0 to 4). Scores are calculated as sum of the respective items for each domain. In addition, a total score summing up all items will be calculated. The scores can only be calculated if no contributing item is missing. Higher scores denote a poorer sleep quality.

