9.4.3.4 Parkinson's Disease Sleep Scale-2 (PDSS-2)

Although a number of scales exist in evaluating sleep disturbance, only 3 are endorsed and recommended by the Movement Disorders Society [53]. One such scale specific for Parkinson's disease is the Parkinson's Disease Sleep Scale (PDSS), and its modified version, the PDSS-2. The purpose of the PDSS-2 scale is to characterize the various aspects of nocturnal sleep problems in PD patients. The PDSS-2 instrument has been shown to be reliable, valid, precise, and a potentially treatment responsive tool for measuring nocturnal disabilities and sleep disorders in PD [54]. PDSS-2 consists of 15 questions evaluating motor and non-motor symptoms at night and upon wakening, as well as disturbed sleep grouped into 3 domains: motor symptoms at night (5 items), PD symptoms at night (5 items), and disturbed sleep (5 items). Specifically, questions assess overall sleep quality, insomnia, sleep fragmentation, Restless Legs Syndrome (RLS) and periodic limb movements of sleep (PLMS), REM (rapid eye movement) sleep behaviour disorder (RBD), hallucinations, nocturia, nocturnal immobility, pain and cramps, morning akinesia, cramps and tremor, and sleep apnea. The PDSS-2 was developed from the PDSS based upon the need for a treatment/measuring tool containing PD-specific sleep disorders. The instrument was extended to address specific sleep disturbances such as RLS, akinesia, pain, and sleep apnea. Daytime sleepiness was removed from the PDSS-2, as it is a more complex PD symptom. To increase ease of use, the visual analogue scale of the PDSS was transformed into a frequency measure in the PDSS-2. The frequency is assessed for the 15 sleep problems based on a 5-point Likert-type scale (ranging from 0 [never] to 4 [very often]). Scores are calculated for each domain as well as a total score. The recall period is for the previous week before the study visit.

9.4.3.5 Questionnaire for Impulsive-Compulsive Disorders in Parkinson's disease- Rating Scale (QUIP-RS)

The QUIP-RS is a fairly novel self-administered rating scale for the evaluation of the symptoms of impulsive compulsive disorders (ICD). ICD may occur in PD patients under dopaminergic drug therapy, also called dopaminergic dysregulation syndrome [55, 56]. QUIP-RS has been shown to have very good sensitivities and appears to be a valid instrument in the evaluation of ICD in patients with APD [57].

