C. Parkinson's Disease Sleep Scale-2 (PDSS-2) Please rate the severity of the following based on your experiences during the past week (7 days). Very often: This mean 6 to 7 days a week Often: This mean 4 to 5 days a week Sometimes: This mean 2 to 3 days a week Occasionally: This mean 1 day a week Never 1. Overall, did you sleep well during the last week? Very Often Often Sometimes Occasionally Never 2. Did you have difficulty falling asleep at night? Very Often Often Sometimes Occasionally Never 3. Did you have difficulty staying asleep? Very Often Often Sometimes Occasionally Never 4. Did you have restlessness of legs or arms at night causing disruption of sleep? ☐ Very Often ☐ Often ☐ Sometimes ☐ Occasionally ☐ Never 5. Was your sleep disturbed due to an urge to move your legs or arms? ☐ Very Often ☐ Often ☐ Sometimes ☐ Occasionally ☐ Never 6. Did you suffer from distressing dreams at night? ☐ Very Often ☐ Often ☐ Sometimes ☐ Occasionally ☐ Never 7. Did you suffer from distressing hallucinations at night (seeing or hearing things that do not exist)? ☐ Very Often ☐ Often ☐ Sometimes ☐ Occasionally ☐ Never 8. Did you get up a night to urinate?

☐ Very Often ☐ Often ☐ Sometimes ☐ Occasionally ☐ Never

9. Did you feel uncomfortable at night because you were unable to turn around in bed or moved due to immobility?
☐ Very Often ☐ Often ☐ Sometimes ☐ Occasionally ☐ Never
10. Did you feel pain in your arms or legs which woke you up while sleeping at night?
☐ Very Often ☐ Often ☐ Sometimes ☐ Occasionally ☐ Never
11. Did you have muscle cramps in your arms or legs which woke you up while sleeping at night?
☐ Very Often ☐ Often ☐ Sometimes ☐ Occasionally ☐ Never
12. Did you wake early in the morning with painful posturing of arms and legs?
☐ Very Often ☐ Often ☐ Sometimes ☐ Occasionally ☐ Never
13. On waking, did you experience tremor?
☐ Very Often ☐ Often ☐ Sometimes ☐ Occasionally ☐ Never
14. Did you feel tired and sleepy after waking in the morning?
☐ Very Often ☐ Often ☐ Sometimes ☐ Occasionally ☐ Never
15. Did you wake up at night due to your own snoring or difficulties with breathing?
☐ Very Often ☐ Often ☐ Sometimes ☐ Occasionally ☐ Never
PDSS-2 © Ray Chaudhuri, Claudia Trankwalder 2010, All rights reserved

D. Beliefs Medication Questionnaire (18-item BMQ)

Your views about medicines prescribed for you.

- We would like to ask you about your personal views about medicines prescribed for you.

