#### Parkinson's disease history

- Time since PD diagnosis calculated as year of visit minus year of PD diagnosis + 1
- Age at PD diagnosis calculated as year of PD diagnosis minus year of birth
- PD motor phenotype
- Time from PD diagnosis to motor fluctuation onset calculated as year of motor fluctuation onset minus year of PD diagnosis +1
- Time from PD diagnosis to start of LCIG calculated as year of first start date of LCIG initiation minus year of PD diagnosis +1
- Morning akinesia (yes, no)
  - If yes: time from PD diagnosis to onset of morning akinesia calculated as year of onset of morning akinesia minus year of PD diagnosis +1
- Wearing off (yes, no)
  - If yes: time from PD diagnosis to onset of wearing off calculated as year of onset of wearing off minus year of PD diagnosis +1
- Dyskinesia present (yes, no)
  - If yes: time from PD diagnosis to onset of dyskinesia calculated as minus year of onset of dyskinesia minus year of PD diagnosis +1

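### Two SAP derivation rules give wrong values as written: PDSS-2 item 1 is summed without reversal, and all six year-based PD durations carry an extra year

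*SAP*

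**What the plan says.** **PDSS-2.** Protocol section 9.4.3.4 gives a single response coding for all 15 items, "ranging from 0 [never] to 4 [very often". The form in Protocol Annex 15, part C, prints item 1 as "1. Overall, did you sleep well during the last week? Very Often Often Sometimes Occasionally Never" and item 2 as "2. Did you have difficulty falling asleep at night? Very Often Often Sometimes Occasionally Never". The options and their order are identical, but the wording runs in opposite directions. SAP section 4.4.4 places items 1, 2, 3, 8 and 14 in the disturbed-sleep domain and adds all 15 items for the total. Its scoring rule is "Scores are calculated as sum of the respective items for each domain" and its direction is "Higher scores denote a poorer sleep quality". It gives the range 0 to 4 without anchors. Neither document mentions reversing an item.

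**Durations.** SAP section 6.3 (Parkinson's disease history) defines "Time since PD diagnosis calculated as year of visit minus year of PD diagnosis + 1". It uses the same form, a difference of calendar years plus 1, for the times from diagnosis to motor fluctuations, LCIG start, morning akinesia, wearing off and dyskinesia. The same list defines "Age at PD diagnosis calculated as year of PD diagnosis minus year of birth", with nothing added, and age under Demographics is also a plain year difference.

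**The concern.** Item 1 is the only PDSS-2 item for which a frequent response is good news. If it enters a plain sum with the other items, good sleep adds points to a score meant to measure bad sleep. The disturbed-sleep domain and the total are then compressed at both ends, and comparisons between the monotherapy groups of SAP section 7.4 can be diluted. The published scores would also not be comparable with correctly scored ones.

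Adding 1 suits an inclusive count of days, where it adds a day. Applied to calendar years it adds a year. The reported disease durations would be too long and would not agree with the ages shown beside them.

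**Working it through.** There is no stated figure to reproduce here, so the rules were applied as written and then corrected.

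**PDSS-2**

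Inputs: coding 0 (never) to 4 (very often) from Protocol 9.4.3.4; item wording from Protocol Annex 15 C; domain membership and plain sums from SAP 4.4.4.

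| Patient | Item 1 | Other items | Disturbed sleep: as written / item 1 reversed | Total: as written / item 1 reversed |
|---|---|---|---|---|
| Best sleeper | 4 | all 0 | 4 + 4×0 = 4 / 0 | 4 + 14×0 = 4 / 0 |
| Worst sleeper | 0 | all 4 | 0 + 4×4 = 16 / 20 | 0 + 14×4 = 56 / 60 |

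For an item 1 response x, the error in either score is x − (4 − x) = 2x − 4, that is −4, −2, 0, +2 or +4.

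Effect on a group comparison, assuming the groups differ by the same amount d on every correctly scored item:

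- Disturbed sleep: 4d − d = 3d instead of 5d, which is 40% smaller.
- Total: 14d − d = 13d instead of 15d, which is 13% smaller.

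The standardised loss is smaller, because the unreversed sum also has a smaller variance. With unit item variances and a common inter-item correlation ρ (an assumption), the correct sum of k items has variance k + ρk(k − 1). The unreversed sum has variance k + ρ[(k − 1)(k − 2) − 2(k − 1)].

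- At ρ = 0.4 and k = 5, the variances are 13 and 6.6. The ratio of standardised differences is (3/√6.6)/(5/√13) = 0.84.
- At ρ = 0.4 and k = 15, they are 99 and 76.6. The ratio is (13/√76.6)/(15/√99) = 0.99.
- At ρ = 0 the variances are equal and the ratios are the raw ones, 0.60 and 0.87.

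**Year-based durations**

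Inputs: the formulas in SAP 6.3.

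1. Internal consistency: (diagnosis − birth) + (visit − diagnosis + 1) = (visit − birth) + 1. For a patient born in 1950, diagnosed in 2005 and seen in 2018, age is 68, age at diagnosis is 55 and time since diagnosis is 14. But 55 + 14 = 69.
2. Against true elapsed time: the error of a plain year difference equals the within-year position of the start date minus that of the end date. It therefore lies between −1 and +1 and averages 0 when both dates have the same mean position in the year. Adding 1 moves the range to 0 to +2 and the mean to +1.
3. Simulation of 1,000,000 pairs (assumed start dates uniform over 10 years, gamma-distributed durations): the plain difference had mean error 0.000 (−0.999 to 0.999). With 1 added the mean error was 1.000 (0.001 to 1.999), and every value was overstated.
4. Regression: three of these durations are candidate predictors in SAP Table 7-2 (diagnosis to LCIG start, to motor fluctuation and to morning akinesia). In a simulated logistic model with 400 patients, adding 1 to the predictor left the slope at −0.09997 and p at 0.000485. Only the intercept moved, from 1.034 to 1.134.

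**The case against.** The strongest point against the PDSS-2 half is that the stored coding is not visible. The SAP gives no anchors for this scale, although it gives them for the PDQ-8, QUIP-RS and BMQ. The PDSS-2 form prints no numbers beside its options, whereas the QUIP-RS form does. The numbers are therefore assigned elsewhere, and a programmer guided by the stated direction could already have stored item 1 reversed. This cannot be excluded, and in that case the defect would be only that the SAP does not say so. But nothing in the documents supports it. The one coding they give, in Protocol 9.4.3.4, covers all items. The SAP says that the QUIP-RS, UPDRS part, NMSS and MMSE scores are calculated automatically in the eCRF, but says nothing of the kind for the PDSS-2. SAP section 2.5 makes the SAP methods binding on the programmer.

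On size, the 40% and 13% figures depend on an equal shift on every item. If the groups do not differ on item 1, the raw difference does not shrink at all. At the assumed correlation of 0.4 the total score loses only about 1% of its standardised difference. That stands.

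On durations, the formula is open and uniform, so an inclusive count of calendar years may have been intended, and a constant cancels from group differences and standard deviations. That also stands. It does not remove the conflict with the two age variables, and an inclusive count of calendar years is not an elapsed time.

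**Conclusion.** Both rules are wrong as written and should be corrected. The PDSS-2 error is between −4 and +4 points per patient, on a 0–20 domain and a 0–60 total. How far it dilutes a group contrast depends on the item pattern and correlation, and is appreciable for the domain and slight for the total under the assumptions above. The conclusion rests on the protocol's coding applying to item 1 as stored.

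All six PD durations exceed the plain year difference by exactly 1 and true elapsed time by 0 to 2 years. The average excess is about 1 year if events have a similar mean position within their calendar years. The contradiction with the ages needs no assumption.

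The reach is limited to descriptive results. The primary monotherapy percentages are untouched, the PDSS-2 is not a predictor in either regression, and the added year leaves odds ratios, p-values and backward selection unchanged.

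**What to change.** - **SAP 4.4.4:** write out the PDSS-2 anchors. Items 2–15: never = 0 through very often = 4. Item 1: very often = 0 through never = 4. State that these values enter the disturbed-sleep and total scores. Before programming, check how item 1 is stored in the eDRF, so that it is reversed exactly once.
- **SAP 6.3:** delete the added 1 from the six durations formed as differences of calendar years. Keep it for inclusive day counts such as titration and LCIG treatment duration. If a count of calendar years touched was really intended, label it as such and do not report it as elapsed time.

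The cost is a few lines of SAP wording, the matching program lines and one look at the database coding. No new data are needed, and no primary or regression result changes.

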#### Beliefs Medication Questionnaire (BMQ)

The BMQ consists of 18 items and is a tool for screening patients' beliefs, attitudes and concerns regarding their medication. For each of the 18 items a 5-point Likert scale is used ranging from 1 (strongly disagree) to 5 (strongly agree).

The BMQ consists of a general section, which assesses general beliefs about medicines, and a specific section which comprises factors assessing beliefs about necessity and concerns about the currently prescribed medications. The general section is sub-divided into two sub-scales: General-Overuse (items 1-4) and General-Harm (items 5-8). The specific section is subdivided into the two sub-scales Specific-Necessity (items 9, 11, 13, 15, 18) and Specific-Concern (items 10, 12, 14, 16, 17). For each sub-scale a score will be calculated as average of the contributing items. The scores can only be calculated if no contributing item is missing.

Higher values of the General-Overuse score indicate a stronger belief that doctors overuse medicines in general. Higher values of the General-Harm score indicate a stronger belief in harm of medicines in general.

Higher values of the Specific-Necessity score indicate a greater perceived necessity of the specific treatment. Higher values of the Specific-Concerns score indicate greater perceived concerns about the specific treatment.

#### 4.4.5 Questionnaires reported by physicians

#### Unified Parkinson's Disease Rating Scale (UPDRS)

The UPDRS is an investigator-used tool to follow the longitudinal course of Parkinson's disease. It includes the five following sections:

- Part I Mentation, Behaviour, and Mood; total score range 0-16
- Part II Activities of Daily Living (ADL); total score range 0-52
- Part III Motor Examination; total score range 0-108
- Part IV Complications of Therapy; total score range 0-23
  - Dyskinesias and Dystonia (Part IV, items 32-35); total score 0-13
  - Motor fluctuations (Part IV, items 36-39); total score range 0-7
  - Other complications (Part IV, items 40-42); total score range 0-3
- Part V Modified Hoehn & Yahr Stage

The scores of the sections part I, part II, part III and part IV as well as the UPDRS total score (total core range 0-199) will be auto calculated in the eCRF.

The sub-scores of part IV will not be auto calculated. Each of these three sub-scores (Dyskinesias and Dystonia, Motor fluctuations, Other complications) will be calculated as the sum of the contributing items.

A sub-score will only be calculated if none of the contributing items is missing. A higher score always indicates a higher impairment.

In addition to the original UPDRS items the duration of dyskinesia and the off period duration were recorded along with item 32 and 39, respectively.

In addition to the scores, the single items 32, 33, 34, 35 and 39 will be analyzed separately (see Section 6.3), including the additionally requested duration of dyskinesia (item 32) and the duration of off period (item 39).

Rating scale part V (Modified Hoehn & Yahr Stage):

UPDRS V consists of one question on the stage of disease. This staging is based on evaluation of PD symptoms, progress and relative level of disability. The UPDRS V score ranges from 0 to 5 with scores of whole numbers as well as 1.5 and 2.5. A higher score indicates a higher stage of disease.

#### Non-Motor Symptoms Scale for Parkinson's Disease (NMSS)

The NMSS is a comprehensive investigator-completed validated tool measuring a broad range of non-motor symptoms in PD patients. The scale is aimed to encompass the whole range of non-motor symptoms experienced by people with PD. The NMSS measures the frequency and severity of these symptoms and comprises 30 questions covering 9 domains of patient symptom experience (cardiovascular including falls, sleep/fatigue, mood/cognition, perceptual problems/hallucinations, attention/memory, gastrointestinal tract, urinary, sexual function, and miscellaneous [pain, taste/smell, weight change, excessive sweating].

The scores of the 9 domains as well as the total score will be auto calculated in the eCRF. The total NMSS score ranges from 0 to 360 with a higher score indicating a higher level of non-motor symptoms burden.

#### Mini-Mental State Examination (MMSE)

The MMSE is a brief, 30-point questionnaire, which provides a quantitative measure of cognitive mental status in adults and is widely used to screen for cognitive impairment and to estimate the severity of cognitive impairment at a given point in time, to follow the course of cognitive changes in a patient over time, and to document response to treatment.

The total MMSE score will be auto calculated in the eCRF.

Any score greater than or equal to 24 points (out of 30) indicates a normal cognition. Below this, scores can indicate severe (0-17 points) or mild (18-23 points) cognitive impairment.

## Healthcare Resource Utilization Questions (HCRU)

The HCRU questionnaire contains questions on the occupational status, nursing home visits, hospitalizations/emergency care visits, caregiver support, and other items with respect to healthcare resource utilization. Ten of the questions the neurologist should discuss with each patient and record the patient's responses. Four questions should be answered by the physician. Each question will be analyzed separately.

#### 4.4.6 Adverse event reporting

The physicians were asked to report product complaints, pregnancies, all adverse events occurring after the time of patient authorization, and all adverse reactions (i.e. adverse events considered as likely related to an Abbvie product) with onset dates prior to patient authorization.

## 5 Analysis data set

One analysis set will be used:

The full analysis set (FAS) consists of all patients enrolled who fulfill the patient selection criteria.

## 6 Variables for analysis

#### 6.1 Site information

- Institution type
- Origin of service
- · Average number of PD and APD patients per year
- Average frequency of routine visits for APD patients on device aided therapy
- Number of specialist physicians working with PD patients
- Support services/functions available at the site (multiple answers)
- Access to invasive treatments (multiple answers)

#### 6.2 Physician's profile

- Therapeutic specialty (type)
- Number of years physician has been working at the institution
- Approximate number of PD patients treated per year
- Approximate number of APD patients treated per year
- Approximate number of APD patients treated with LCIG per year
- Use of standard treatment algorithms/established guidelines/definitions of PD treatment (yes, no)
  - If yes: specification (multiple answers)
- Overall treatment preference
- Years of DBS experience
- Number of DBS patients
- Years of CSAI experience
- · Number of CSAI patients

Years of LCIG experience

